Symptom Measure, consisting of 23 questions assessing mental health domains, and the Positive Negative Affect Schedule. PTSD symptoms will be assessed with the PTSD Checklist-5 and the Childhood Trauma Questionnaire will query specific types of PTSD-related events. c) Repetitive negative thinking: Ruminative Response Scale (RRS) includes 22 items about tendencies to dwell on negative thoughts during periods of low mood; and the Penn State Worry Questionnaire (PSWQ) includes 16 items assessing pathological worry; the RNT-10 will be given at the screening visit; the Attention Control Scale will assess difficulty controlling thought content. The emotion regulation questionnaire will assess how participants attempt to control/regulate negative thoughts. D) Physical health and pain: WHODAS will be used to assess current self-rated health, the Insomnia Severity Index will evaluate sleep. e) drug and alcohol screening: the AUDIT, DAST, and PhenX nicotine screeners will be used to evaluate substance use; f) Cognitive assessments: Test My Brain assessments. These tasks ask participants to attend to, memorize, and process stimuli to measure neuropsychological abilities, and include the following tests:

Matrix Reasoning – test of the ability to identify “rules” to a puzzle (viewing a series of visuospatial patterns) and guess the next right answer.

Digit span – assesses working memory and attention. Digits are presented which the participant must repeat back.

Trail making task – measures executive functioning. Participants must draw a line between numbers and letters that are presented in random spatial locations, in the correct serial order.

Digit symbol matching – measures processing speed. Participants are shown a series of digits and must fill in the matching symbol using a “code” provided.

Participants will complete a modified Treatment Credibility Questionnaire for qualitatively assessing acceptability, satisfaction, and feedback about design features. All questionnaires and interviews administered are validated/published measures.

Baseline Visit and Post Visit 2: During the Baseline Visit, further cognitive assessments will be administered. NIH Toolbox Cognition Battery and a computer administered Operation Span task will be administered to further characterize cognitive functioning. This includes the following tests.

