COGENT, dose, and randomization: Following the baseline assessments, participants will be randomized to receive COGENT for 4 weeks (n=32) or an assessment-only control condition that receives clinical, cognitive, and MRI assessments at the same time points (n=32), stratified by diagnostic category (primary mood vs. primary anxiety/traumatic stress). In the basic COGENT training program framework, participants will view a series of items to be remembered, following by a secondary processing task where sentence puzzles are

solved. Participants will receive feedback about their accuracy at the conclusion of each set, and an adaptive algorithm will be used to ensure enough difficulty is maintained. The algorithm titrates advancement to the next trial based on meeting at least 85% accuracy on the prior set of trials. Our preliminary data indicate that a session frequency of 8 sessions, delivered twice weekly for 4 weeks (approximately 30 minutes per session) sufficiently improved cognitive performance. Participants assigned to COGENT will be randomized to complete dosing previously established in our work, 8 sessions over 4 weeks or a dosing of 16 sessions over 4 weeks based on literature indicating that training durations of 8 hours may be most effective. Randomization will be generated by [name] and will be securely transmitted to the study coordinator. Task-based adherence data will be collected (number of sessions, frequency). Participants assigned to waitlist will be given the option to complete COGENT after all assessments if they wish.

COVID-19 Considerations: During the COVID-19 crisis, participants may be asked to complete the consenting, screening and screening measures, and cognitive paradigms using HIPAA compliant UCSD Zoom telehealth technology to minimize in-person contact. For in-person tasks, all UCSD and Keck safety procedures will be implemented based on the current Ramp Up phase.

Clinical monitoring: We will administer a brief questionnaire at the treatment mid-point, including the GAD7, PhenX depression, and RNT-10 for purposes of identifying individuals with increased symptoms. Any individual reporting >20% increase in inventories will be referred to the PI for evaluation per the Risk Management plan below.

Table: Assessments by visit	Active groups	Waitlist group

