Screening visit MINI CSSRS MRI safety OSU-TBI RNT-10 Demographics GAD-7 Phenx Depression PhenX DSM RRS PSWQ WHODAS CTQ PANAS ACS ERQ PCL-5 AUDIT/DAST/Phenx Nicotine ISI Suicide Cognitions Treatment credibility	X	x
Midpoint clinical check GAD7 Phenx Depression RNT-10	X	
Baseline visit Cognitive assessments MRI	X	X

Cognitive training	X	
Post visit 1 (same as screening visit)	X	X
Post visit 2 (same as baseline visit)	X	X

STATISTICAL DESIGN AND POWER

Primary outcomes: Change in working memory and repetitive negative thinking. To determine whether COGENT engages the target as hypothesized (i.e., improving Ospan behavioral performance), we will analyze the effect of COGENT versus the control on the Ospan total correct score in a 2 (group: combined COGENT conditions, control) x 2 (time: pre-training, post-training) analysis of variance (ANOVA). Our hypothesis will be supported by a significant training by time interaction effect ($p < .05$; medium-large effect size based on power calculations). To investigate optimal dosing of COGENT training, effect size estimates will be compared by dose (8 vs. 16 sessions) for differences in mean change pre- to post-training. This analytic approach will be repeated for the RNT-10 Repetitive Negative Thinking and other symptom measures.

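### Both primary outcomes are tested on raw change; the test is valid, but adjusting for the pre-randomisation score would usually recover power at almost no cost, by an amount that depends on correlations and SDs the plan does not give

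*Combined protocol and SAP*

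**What the plan says.** Under Statistical Design and Power in section 9 of the combined protocol and SAP, the Ospan total correct score is tested through the group-by-time interaction of a "2 (group: combined COGENT conditions, control) x 2 (time: pre-training, post-training) analysis of variance (ANOVA". For the second primary outcome, "This analytic approach will be repeated for the RNT-10 Repetitive Negative Thinking and other symptom measures". For dose, "effect size estimates will be compared by dose (8 vs. 16 sessions) for differences in mean change pre- to post-training". Support for the hypothesis is tied to p<.05 and a "medium-large effect size based on power calculations". No numeric effect, power, SD or pre-post correlation is given, and no covariate is named for these analyses. The only mixed model in the plan is for the fMRI data.

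The timing is set out earlier in section 9. "Following the baseline assessments, participants will be randomized to receive COGENT for 4 weeks (n=32", against 32 controls, and allocation is "stratified by diagnostic category (primary mood vs. primary anxiety/traumatic stress". At the Baseline Visit, "a computer administered Operation Span task will be administered to further characterize cognitive functioning". For the symptom outcome, "the RNT-10 will be given at the screening visit", and the visit table repeats each set of measures after training. Entry is decided on a separate telephone administration of the same questionnaire, with a score above 32 required. Section 10 plans to randomise 75 participants for 65 evaluable.

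**The concern.** With two visits, the interaction test is identical to a two-sample t-test on post minus pre. That fixes the slope of post on baseline at 1. Unless the true slope is close to 1, part of the baseline variation is carried into the comparison as noise. ANCOVA estimates the slope instead. The covariate it needs is already collected, for both outcomes, before allocation.

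What is at stake is efficiency. With about 32 per arm, a gain worth 10 or 20 participants could not easily be had any other way. The same loss widens the 8 vs. 16 session comparison, which has about 16 per dose if the 32 are split equally. The choice also has to be made in advance: a switch from change scores to ANCOVA after the data are seen would look data-driven.

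**Working it through.** **The plan's own figure.** There is no numeric power calculation to reproduce. As a plausibility check, 32 per arm at two-sided 0.05 detects 0.71 SD of change with 80% power (noncentral t). That is compatible with a medium-to-large effect but confirms no stated figure.

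**Inputs.** From the plan: 32 vs. 32, alpha 0.05, two visits, one two-level stratum. Assumed: a two-sided test, rho from 0.3 to 0.9, and k = SD(post)/SD(pre) from 0.8 to 1.2. The unit is the baseline SD.

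**Formulas.**
- Change score: variance 1 + k² − 2·rho·k, which is 2(1 − rho) when k = 1; 62 df.
- ANCOVA with baseline and stratum: variance (1 − rho²)k² × (1 + 1/60); 60 df. The last factor is the cost of estimating the slope. A balanced stratum costs one degree of freedom.
- Equivalent N: the size at which the change-score test would reach the power ANCOVA has at 64, starting from an effect that gives the planned test 80%.

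**Worked case, rho = 0.5, k = 1.** The change variance is 2 × 0.5 = 1.00, so 80% power needs a difference of 0.711. The ANCOVA variance is 0.75 × 61/60 = 0.7625. Power for the same difference is 89%. The planned test would need about 83 participants to match, which is 19 more than 64.

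**Ospan, extra participants the planned test would need:**

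| Post/pre SD ratio | rho 0.3 | rho 0.5 | rho 0.7 | rho 0.9 |
|---|---|---|---|---|
| 0.8 | 59 | 45 | 35 | 38 |
| 1.0 | 32 | 19 | 10 | 2 |
| 1.2 | 18 | 8 | 1 | 0 |

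In the equal-SD row, 80% power becomes 93, 89, 85 and 81%. For a raw difference of 0.5 SD in that row, power goes from 38 to 53%, 50 to 62%, 72 to 78%, and stays at 99%.

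**Where the gain disappears.** Before the slope cost, the variance ratio (1 − rho²)k²/(1 + k² − 2·rho·k) reaches exactly 1 at k = 1/rho, where the true slope is 1. At rho 0.9 that is k = 1.11, so over k from 0.8 to 1.2 the ratio runs from 0.61 to 1.00. With the cost, the peak is 61/60 = 1.017, and 80% power becomes about 79%.

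**RNT-10.** Participants are selected on the telephone score, so the spread at screening may be narrowed more than the spread after training. Assume normal scores, the top fraction p kept, correlation q between telephone and screening scores, and correlation rho of each with the post score before selection. Let c be the cutoff, λ = φ(c)/p and δ = λ(λ − c). After selection, Var(baseline) = 1 − q²δ, Var(post) = 1 − rho²δ and Cov = rho − q·rho·δ.

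Example with p = 0.5, rho = 0.7, q = 0.9:
- δ = 0.637, giving variances 0.484 and 0.688 and covariance 0.299.
- Change variance: 0.484 + 0.688 − 2 × 0.299 = 0.574.
- ANCOVA variance: 0.688 − 0.299²/0.484 = 0.503.
- Ratio 0.88, or 0.89 with the slope cost. Power goes from 80 to 84%, worth about 7 participants.

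Over p from 0.15 to 0.5, rho from 0.5 to 0.7 and q from rho to 0.9, the ratio after cost is 0.70 to 0.89, power becomes 84 to 92%, and the gain is about 7 to 27 participants. At q = 0.9 it is about 7 to 11.

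**Dose comparison, assuming 16 per dose and equal SDs.** The 95% half-width on raw change is 0.85, 0.72, 0.56 and 0.32 SD at rho 0.3, 0.5, 0.7 and 0.9. Adjusted, it is 0.70, 0.64, 0.53 and 0.32 SD.

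**Validity.** In 20,000 simulated trials with no effect, the change-score test rejected 4.6% of the time at rho 0.3 and 5.1% at rho 0.7.

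**The case against.** The strongest reply is that a 2 x 2 interaction test is an accepted analysis that holds its level, and that the gain rests on two quantities absent from the documents. Both parts are true. If the post SD is somewhat larger than the pre SD and the correlation is high, there is nothing to gain and up to about one point of power to lose. The gain also shrinks when power is already high: for a raw difference of 0.8 SD with equal SDs it is about 7 points at rho 0.5 and about 1 at rho 0.7. For RNT-10, selection on a closely related telephone score pushes the benefit to the low end. The slope cost above assumes a balanced stratum; if an unbalanced stratum is charged as well, the equal-SD gains at rho 0.3 and 0.7 fall to about 30 and 8.5.

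A second reply is that adjustment is not neutral towards missing data. In simulations with 38 and 37 randomised, no true effect, rho 0.5 and loss driven by the post score (log-odds 1.2 per SD), bias goes from −0.05 to −0.08 SD when losses split 7/3. When all 10 fall in one arm it goes from −0.12 to −0.19 SD, and false positives go from 7.9 to 13.7%. If loss depends on the baseline score instead, adjustment removes a bias of 0.13 SD in the 10/0 case. Loss therefore favours neither method overall, but the risk is real and calls for a sensitivity analysis.

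A reader might also infer that leaving out the stratum invalidates the test or costs much of the power shown here. Neither follows. With balanced strata, adding the stratum to ANCOVA leaves the true sampling variance unchanged. If strata differ by 0.5 SD in change, the planned test is slightly conservative (4.0 to 4.5%). Including the stratum aligns the analysis with the randomisation and corrects the standard error; no gain above is credited to it.

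**Conclusion.** The planned test is valid, and for both primary outcomes it usually gives up power that data collected before randomisation would supply. For Ospan with equal SDs the loss is worth about 32, 19, 10 and 2 participants at rho 0.3, 0.5, 0.7 and 0.9. It is smaller, down to nothing, if the SD rises after training, and larger if the SD falls. For RNT-10 it is about 7 to 27 under the selection model. All of these rest on assumed correlations and SDs and on 32 analysed per arm.

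Two stronger readings should be resisted. The trial cannot be called underpowered on this ground, because the plan states neither a numeric effect nor a power. And no single range covers both outcomes, because RNT-10 entry is selected on an earlier score and Ospan entry is not. This is a recommended improvement in efficiency, not a correction of an error rate.

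**What to change.** Make the primary analysis of Ospan total correct and of RNT-10 an ANCOVA of the post-training score on group, baseline score and diagnostic stratum, at two-sided 0.05. Use the Baseline Visit Ospan and the screening-visit RNT-10 as baselines, not the telephone score used for entry. Report the 8 vs. 16 session comparison as the baseline-adjusted difference with its 95% interval; even adjusted, that interval stays wide. Add one prespecified sensitivity analysis, such as a delta adjustment, for the roughly 10 losses expected (75 − 65).

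The cost is SAP wording and two degrees of freedom (62 to 60). No new data, visits or participants are needed. The downside is the possible increase in bias if loss depends on the post score, which the sensitivity analysis is there to examine.

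Two drafting notes, separate from this point: state which SD standardises the effect-size benchmark, and align the 64 (32 + 32) in section 9 with the 65 and 75 in section 10.

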6. SPECIFIC AIMS

Improving control over working memory interference is theorized to be the most effective executive functioning manipulation for targeting clinical symptoms for mood, anxiety, and traumatic stress disorders. We will test whether two doses of COGNitive Enhancement Training (COGENT; 8 vs. 16 sessions) modify control over working memory interference across multiple units of analysis as compared to a no-training control condition.

Aim 1: Identify the cognitive effects and optimal dose of COGENT to improve executive functioning measured behaviorally (cognitive task) and neurally (fMRI). We hypothesize that individuals completing COGENT will show improved executive functioning on behavioral and neural measures relative to those assigned to the waitlist condition. An effect size benchmark will be used to evaluate whether there is added

benefit to completing more training sessions (16 versus 8) over the four week period to evaluate optimal dosing.

Aim 2: Evaluate the clinical effects of the COGENT program. We hypothesize that individuals completing COGENT will show a reduction in repetitive negative thinking. We will assess whether there are additional reductions in mood and anxiety symptoms.

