Group level analyses- the outcomes for the fMRI tasks are the difficulty regressor for the Rspan and emotional working memory tasks. The data will be entered into a mixed effects model, which offers a flexible framework to model the sources of variation and correlation that arise from grouped data (AFNI 3dLME). Once voxel-wise statistics have been calculated, we will use a threshold adjustment based on Monte-Carlo simulations in *a priori* functional regions of interest (ROIs) defined by neuroanatomical atlases of the frontoparietal circuit (NeuroSynth v5 "working memory" Topic 045) with FDR correction ($p < .05$) to guard against identifying false positive activations. The linear mixed effects model will include Group (COGENT vs. control) and Condition (interference vs. baseline) as between-subject factors and Time (pre-training, post-training) as the within-subjects factor, with subject included as a random factor.

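### Aim 1 seeks an optimal dose tested against no training, but no planned analysis reports either dose against control with a confidence interval

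*Combined protocol and SAP*

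**What the plan says.** Section 6 (Specific Aims) says both doses, 8 and 16 sessions, will be tested "as compared to a no-training control condition". Aim 1 then turns to the choice between them: "An effect size benchmark will be used to evaluate whether there is added" benefit from 16 sessions rather than 8. No value is given for that benchmark.

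Section 9 (Statistical Design and Power) analyses the Ospan total score as a "2 (group: combined COGENT conditions, control) x 2 (time: pre-training, post-training") ANOVA. The success criterion is "Our hypothesis will be supported by a significant training by time interaction effect" at the .05 level, with a "medium-large effect size based on power calculations". For dosing, "effect size estimates will be compared by dose (8 vs. 16 sessions) for differences in mean change pre- to post-training". The scheme extends to the clinical outcomes: "This analytic approach will be repeated for the RNT-10 Repetitive Negative Thinking and other symptom measures".

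The fMRI group-level model has the same two-level structure: "The linear mixed effects model will include Group (COGENT vs. control"), with no dose term. Yet the lay summary (Section 5) and Aim 1 both base the dose question on behavioral and neural measures.

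The paragraph on COGENT, dose and randomization in Section 9 gives 32 participants to COGENT and 32 to control, without stating how the 32 are split by dose. It cites preliminary data that 8 sessions improved cognitive performance.

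**The concern.** The aims set up three groups and the analysis uses them in two separate steps. In one, control is set against a mixture of the doses. In the other, the doses are set against each other. Neither step reports how a single dose compares with control.

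A significant pooled result can come mostly from one dose. A small 16-versus-8 difference can mean that both doses work equally well, that neither works, or that the difference was poorly estimated. Pre-post change within a dose arm does not settle this, because it also contains practice effects on Ospan and, for a sample selected on high repetitive-thinking scores, regression to the mean. Only the contrast with control removes those.

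At stake is the dose conclusion of Aim 1. A schedule could be carried forward as optimal with no interval in the report showing that it beats no training.

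**Working it through.** **Inputs.** From Section 9: 32 COGENT, 32 control, significance level .05. Assumed because not stated: a 16/16 split by dose, two-sided testing, SD of change equal to 1, normal outcomes, and benchmarks of 0.2, 0.5 and 0.8 SD. With two time points, the group-by-time interaction is a two-sample test on change scores.

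**The plan's own figure.** No power, SD or numerical effect is given, so there is nothing to reproduce exactly. As a consistency check, 32 versus 32 gives 80% power at d = 0.71 (t-based), which fits the medium-large description. The pooled test is sized as described.

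**Precision of each contrast.** SE = sqrt(1/n1 + 1/n2).

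| Contrast | n | SE | 95% CI half-width | Power at d = 0.5 / 0.7 / 0.8 |
|---|---|---|---|---|
| Pooled vs control | 32 vs 32 | 0.250 | 0.50 | 50% / 79% / 88% |
| One dose vs control | 16 vs 32 | 0.306 | 0.62 | 36% / 61% / 73% |
| 16 vs 8 sessions | 16 vs 16 | 0.354 | 0.72 | 28% / 48% / 59% |

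**Link between the planned contrasts.** Let P be the pooled effect against control and D the 16-minus-8 difference. With equal dose groups, the 8-session effect against control is P − D/2 and the 16-session effect is P + D/2. The variance agrees: 1/16 + (1/8)/4 = 3/32, and sqrt(3/32) = 0.306.

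**Illustration: 8 sessions d = 0, 16 sessions d = 0.8.** The expected pooled effect is (0 + 0.8)/2 = 0.4, against the roughly 0.50 needed for significance. In simulation (100,000 and 200,000 trials) the pooled test favours training significantly in 32% of trials.

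| Benchmark | Pooled test significant and D below benchmark, share of all trials | Share of pooled-significant trials | Same, also requiring the 8-vs-control CI to exclude zero |
|---|---|---|---|
| 0.2 | about 2% | about 5% | about 3% |
| 0.5 | about 7% | 21–22% | 5–6% |
| 0.8 | 16–17% | 51–53% | 7–8% |

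The ranges reflect simulation variation and whether D is divided by the true or the estimated SD.

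**Would a positive point estimate be enough?** No. After a significant pooled test P is at least about 0.50, so if D is below benchmark b the observed 8-session effect is at least about 0.50 − b/2: 0.40, 0.25 or 0.10 SD. It is positive almost by construction. In simulation, requiring only a positive estimate left the error shares unchanged. Requiring the interval to exclude zero is what reduces them.

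**Price of the interval rule.** If both doses truly have d = 0.7, D falls below the benchmark in about 72%, 92% and 99% of pooled-significant trials. Adding the interval requirement lowers the share in which 8 sessions is named to about 63%, 73% and 75%.

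**The case against.** The strongest reply is that the 8-session effect can be recovered from the two planned contrasts, as P − D/2. That is correct, exactly so with equal dose groups. A reader might infer that the plan leaves the effect impossible to estimate, and it does not. What is missing is a planned report of it with an interval.

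Second, a reader might infer that the plan contains a rule that defaults to 8 sessions whenever 16 adds too little. No such rule is written. Section 6 speaks of evaluating added benefit and Section 9 of investigating dosing. Nothing makes the dose reading conditional on the pooled test either. The two-step sequence in the illustration is one plausible use of the plan, not its text.

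Third, the 51–53% figure is tempting as a headline. It is conditional on a significant pooled test, and it arises because the assumed benchmark equals the assumed true difference, so about half of all estimates fall below it. The share of all trials is 16–17%. An inactive 8-session schedule is also pessimistic, given the preliminary data cited in Section 9. Those data are from outside this trial, however, and Section 8 of the argument for the study, in the background, presents this as a broader transdiagnostic group than was tested before.

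Fourth, the dose wording might be read as each dose's effect relative to control. The sentence names only 8 versus 16 and defines the effect as a difference in pre-post change, so the text does not say that.

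Finally, silence on the benchmark's value does not show that it will be chosen after the data are seen. It shows only that the plan does not rule this out.

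**Conclusion.** The concern holds as a gap between Aim 1 and its analysis. The aim promises each dose against no training; Section 9 specifies only pooled doses against control and one dose against the other, and the fMRI model has no dose term. A dose could therefore be described as optimal without a reported contrast with control to support it.

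The size is moderate and depends on the unstated benchmark: about 2%, 7% or 17% of all trials in a pessimistic scenario, under an assumed 16/16/32 split, SD of change 1 and benchmarks of 0.2, 0.5 and 0.8. The pooled primary test is not called into question. The change should be made because it is almost free and bears directly on what Aim 1 can conclude.

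**What to change.** 1. In Statistical Design and Power, fit the Ospan model with three groups (8 sessions, 16 sessions, control). Keep the pooled contrast as the primary test. From the same fit report 8 versus control, 16 versus control and 16 versus 8, each with a 95% CI.
2. State that a training schedule will be described as established as optimal only if the CI for its own contrast with control excludes zero, and that not established is an allowed conclusion.
3. Write the numerical benchmark for 16 versus 8 into the plan before any outcome data by arm are examined.
4. Use the same three-level group factor in the fMRI group-level model. The documents tie the dose question to behavioral and neural measures, so the dose question should not be confined to Ospan.

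The cost is protocol wording and extra contrasts from data already being collected, with no added participants or visits. The downside is imprecision. With about 16 against 32, each dose-versus-control interval is about ±0.6 SD and power is about 61% at d = 0.7, so a schedule that works may go unconfirmed and the trial may have to report that neither is established as optimal.
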